9.9 Health Economics OR Medical Resource Utilization and Health Economics

In addition to the aforementioned [REDACTED], health care resource utilization data will be collected for Part 2 participants using an internal case report form eCRF developed for use in previous trials. The form, which is completed by study staff, records information about hospital admissions, including number of days spent in various wards and discharge diagnosis, as well as non-protocol specified visits related to study therapy, including date of visit, reason for visit, and type of visit. The health care resource utilization data will be used to support subsequent economic evaluations.

10 STATISTICAL CONSIDERATIONS

10.1 Sample Size Determination

This study will consist of multiple cohorts/parts for different target populations with different treatment regimens and the sample size for each part has been provided as below.

10.1.1 mCRC 3rd line Participants: Part 1 Dose Optimization Cohorts

Sample size at each dose level depends on the observed toxicity and is not based on statistical considerations. Three to 6 participants will be evaluated at each dose level. Administration of treatment regimen to 6 participants at a dose level provides ~82% probability of observing at least one occurrence of any adverse event if there is a 25% incidence in the population from which the sample is drawn. Approximately 3 to 18 participants are estimated to be treated in these dose optimization cohorts. The total sample size for this part ranges from 3 to 18 participants.

10.1.2 mCRC 3rd line Plus Participants: Part 2 [REDACTED] Cohort

The purpose of Part 2 is to gather tolerability and preliminary efficacy, for nivolumab in combination with ipilimumab and trametinib or SOC (regorafenib) in pMMR/MSS 3L+ (no more than 4 prior lines of therapy) mCRC, including [REDACTED]

[REDACTED] for combination therapy with immune checkpoint inhibitor(s) and MEK inhibitor. Approximately 120 participants will be randomized in 2:1 ratio to receive nivolumab plus ipilimumab plus trametinib continuous dosing (Cohort 4), or SOC (regorafenib, Cohort 5).

10.1.3 mCRC 2nd line Participants: Part 1A Dose Optimization Cohorts

Sample size at each dose level depends on the observed toxicity and is not based on statistical considerations. Three to 6 participants will be evaluated at each dose level. Administration of treatment regimen to 6 participants at a dose level provides ~82% probability of observing at least one occurrence of any adverse event that would occur with a 25% incidence in the population from which the sample is drawn. Approximately 3 to 12 participants are estimated to be treated for each of two dose optimization cohorts (nivolumab + ipilimumab + continuous trametinib dosing and nivolumab + ipilimumab + intermittent trametinib dosing). The total sample size for this part ranges from 6 to 24 participants.

10.1.4 mCRC 2nd line Participants: Part 1B [REDACTED] Cohorts

The safety and efficacy of the triplet combination regimen has been initially explored in the 2L setting. An additional [REDACTED] cohort will be initiated for the 2L participants to further optimize the patient selection strategy. Approximately 80 participants will be treated to establish expanded experience with the triplet regimen of nivolumab plus ipilimumab plus trametinib continuous dosing.

10.2 Populations for Analyses

For purposes of analysis, the following populations are defined below. The population definition will apply to all cohorts unless specified otherwise:

Population	Description
Enrolled	All participants who sign informed consent and were registered into IRT.
Randomized	All participants who are randomized to any treatment in Part 2 (primary efficacy analysis population for Part 2 and outcome research assessment analysis population for Part 2).
Treated	All participants who take at least 1 dose of study medication.
Response-evaluable	All treated (randomized for Part 2) participants with measurable disease at baseline and at least one post-baseline tumor assessment.

Population	Description

10.3 Statistical Analyses

The statistical analysis plan will be developed and finalized before the first database lock and will describe the selection of participants to be included in the analyses, and procedures for accounting for missing, unused, and spurious data. Part 1A/1B, Part 1 and Part 2 will be analyzed independently. Below is a summary of planned statistical analyses of the primary and secondary endpoints.

A description of the participant population will be included in the statistical output reported, including subgroup of age, gender, and race.

10.3.1 Efficacy Analyses

The primary efficacy analyses will be performed on the treated population for all cohorts, except for Part 2 where the primary efficacy analyses will be performed on the randomized population. Efficacy in subgroups of interest will be evaluated in Part 2 and in Part 1B.

Other subgroups (e.g., the stratification factor of tumor sidedness, etc.) will be described in the Statistical Analysis Plan (SAP). Details on censoring scheme on time-to-event endpoints such as DOR, PFS, and OS and additional analyses will be described in the SAP. In Part 2, no crossover will be permitted between the two treatment arms upon discontinuation of study treatment.

Endpoint	Statistical Analysis Methods
Best Overall Response (BOR) for a participant will be assessed per RECIST 1.1 as applicable per investigator (primary endpoint). BOR is defined as the best response designation, recorded between the first dosing date (randomization date, for Part 2) and the date of the initial objectively documented tumor progression per RECIST v1.1 or the date of subsequent therapy, whichever occurs first. For participants without documented progression or subsequent therapy, all available response designations will contribute to the BOR determination. ORR is defined as the proportion of all treated (randomized, for Part 2) participants whose BOR is either confirmed complete response (CR) or confirmed partial response (PR). The disease control rate (DCR) is defined as the proportion of participants whose BOR is either confirmed CR or confirmed PR or stable disease (SD)	
Estimate of ORR/DCR and corresponding two-sided exact 95% CI using the Clopper-Pearson method by treatment
DOR and TTR (per investigator) DOR for a participant with a BOR of confirmed CR or PR, is defined as the time between the date of first confirmed response and the date of the first objectively documented tumor progression per RECIST 1.1 or death, whichever occurs first. The rules of censoring are the same as for PFS. Time to response (TTR) is defined for participants who had a confirmed CR or PR as the time from the first dosing date (randomization date, for Part 2) to the date of first documented CR or PR per RECIST 1.1.	
Estimate of median DOR/TTR using the Kaplan-Meier method and corresponding two sided 95% CI (using log-log transformation) by treatment
Progression Free Survival PFS (per investigator) and overall survival OS PFS for a participant is defined as the time from the first dosing date (randomization date for Part 2) to the date of first objectively documented disease progression per RECIST 1.1 (ie, radiologic) or death due to any cause, whichever occurs first. Participants who die without a reported prior progression and without initiation of subsequent anti-cancer therapy will be considered to have progressed on the date of their death. 
Participants who did not progress or die will be censored on the date of their last tumor assessment.Participants who did not have any on study tumor assessments and did not die will be censored on the first dosing date (randomization date, for Part2).Participants who started any subsequent anti-cancer therapy without a prior reported progression or prior to death will be censored	
Estimate of median and rates at fixed time points by the Kaplan-Meier method and corresponding two sided 95% CI using log-log transformation (for median) and Greenwood formula (for rates) by treatment

Endpoint	Statistical Analysis Methods

at the last tumor assessment prior to initiation of the subsequent anticancer therapy.
 
Further explanation for various censoring scenarios for PFS will be specified in the SAP. 
OS for a participant is defined as the time from the first dosing date (randomization date for Part 2) to the date of death due to any cause. A participant who has not died will be censored at last known date alive.
	

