Trametinib 1.5 mg QD was the starting dose selected for Cohort 1, 2, and 3 groups. In Part 1, trametinib continuous dosing regimen were investigated initially in Cohort 1, with dose de-escalation and escalation scheme built in for trametinib intermittent dosing regimen, 2 week ON/2 week OFF (Cohort 1 Group). In Part 1A, both trametinib continuous dosing and intermittent dosing was investigated initially in two separate Cohort Groups (Cohort 2 Group and Cohort 3 Group). Specifications regarding trametinib dosing in dose optimization phase can be found in [Section 5.1.1](#).

The totality of the safety data was reviewed, and decision on dose escalation, de-escalation or discontinuation of a particular dosing regimen were made by the study team in conjunction with treating physicians and documented accordingly.

[figure not shown]
- For [REDACTED] | [REDACTED] **(Part 1B) phase**, further evaluations of safety and efficacy will be conducted in Part 1B (triplet regimen; 2L pMMR/MSS mCRC) of the study. Participants who have failed 1 prior line of therapy will be allocated to:
 - Part 1B Cohort 6: One cohort will be initiated in Part 1B to further characterize the safety and preliminary efficacy profile of the triplet regimen. Participants with 2L pMMR/MSS mCRC will be assigned to receive: 6 mg/kg nivolumab (Q4W) plus ipilimumab 1 mg/kg (Q8W) plus trametinib 1.5 mg continuous QD (Cohort 6)
- For [REDACTED] | [REDACTED] **(Part 2) phase**, the efficacy and safety of the investigational triplet regimen versus SOC regimen (regorafenib) in 3L+ (no more than 4 prior lines of therapy) pMMR/mCRC will be evaluated in Part 2, the randomized controlled portion of the trial.
 - Participants will be randomized at 2:1 ratio to receive nivolumab 6 mg/kg Q4W plus ipilimumab 1 mg/kg Q8W plus trametinib 1.5 mg continuous QD (Cohort 4), OR regorafenib in the SOC arm (Cohort 5).

For Part 1B (Cohort 6) and Part 2 (Cohorts 4 and 5), the proportion of participants with RAS mutations will be monitored on an ongoing basis. The IRT system will be set up to notify the Sponsor once the pre-defined number of RAS mutant participants have been enrolled. The target will be approximately 65% mutant, 35% wild type. If accrual diverges significantly from this goal, accrual in a cohort may be paused after discussion between the Sponsor and the investigators. Patients with BRAF V600 mutation are not eligible for the study.

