Preliminary safety, efficacy, [REDACTED] data from Parts 1 and 1A were analyzed in a predetermined interim analysis to select the optimal dosing regimen of nivolumab 6 m/kg Q4W plus ipilimumab 1 mg/kg Q8W plus trametinib 1.5 mg continuous QD for Part 1B. Approximately 80 participants (Cohort 6) will be treated in Part 1B to further assess the safety and preliminary efficacy of the combination regimen. The totality of the safety data and preliminary efficacy data from Part 1B will be reviewed on an ongoing basis.

5.1.3 *Part 2: [REDACTED] the Triplet Regimen and Standard of Care Arm*

Preliminary safety, efficacy, [REDACTED] data from Part 1 and Part 1A were analyzed in a predetermined interim analysis to determine the optimal regimen for Part 2. Part 2 of the study for

the triplet regimen will consist of 1 cohort (Cohort 4) to investigate the safety and clinical activity of nivolumab 6 mg/kg Q4W plus ipilimumab 1 mg/kg Q8W plus trametinib 1.5 mg continuous QD. A SOC arm with regorafenib will also be initiated (Cohort 5). Participants will be randomized according to a 2:1 ratio (approximately 80 participants to receive the triplet regimen and 40 participants to receive the SOC therapy, regorafenib).

Participants who have failed at least 2 prior lines of therapy (no more than 4 prior lines) will be randomized to receive the triplet regimen OR regorafenib. No crossover will be permitted between the 2 treatment arms upon discontinuation of study treatment.

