Trametinib Dose Level (DL)	Trametinib Dose in Doublet Regimen ^a --- Cohort Number	Trametinib Dose in Triplet Regimen ^b - Continuous Dosing --- Cohort Number	Trametinib Dose in Triplet Regimen ^b Intermittent Dosing --- Cohort Number
Parts 2 and 1B			
Trametinib Dose Level (DL)	Regorafenib	Trametinib Dose in Triplet Regimen ^b - Continuous Dosing --- Cohort Numbers	
N/A		Part 2 1.5 mg continuous --- Cohort 4 Part 1B 1.5 mg continuous --- Cohort 6	
SOC without trametinib	Part 2 with regorafenib --- Cohort 5	NA	

DL= dose level; SOC=standard of care; wk=week.

^a Doublet regimen: nivolumab + trametinib. Refer to [Section 7.1.3](#) and [7.1.4](#) for nivolumab dosing.

^b Triplet regimen: nivolumab + ipilimumab + trametinib. Refer to [Sections 7.1.5](#) and [7.1.6](#) for nivolumab and ipilimumab dosing.

Part 2 is a randomized open-label study with 2 treatment arms, nivolumab + ipilimumab + trametinib versus regorafenib. Enrollment is closed for Part 2.

- Once enrolled in IRT, participants who have met all eligibility criteria for Part 2 will be randomized in a 2:1 ratio to nivolumab + ipilimumab + trametinib (Cohort 4) or regorafenib (Cohort 5). The following stratification factors will be applied:
 - Primary tumor sidedness (left vs right) ([Appendix 13](#)). Participants with unknown primary tumor location or primary tumor located in both sides will be allocated to the right sided stratum. Such participants are not expected to exceed 2% to 5%.
 - Extended RAS mutation status (wild-type vs mutant). Please refer to [Section 5](#) for details on proportion of participants with RAS mutation status monitoring. Patients with unknown RAS/BRAF status will not be eligible. Patients with BRAF V600 mutation are not eligible for the study.

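### The visible Section 10.3.1 methods summarise each Part 2 arm separately; a stratified between-arm estimate would make use of the randomization and should be added or cited

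*Combined protocol and SAP*

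**What the plan says.** Section 5.1 presents Part 2 as the randomized controlled portion of the trial, which is to evaluate "the efficacy and safety of the investigational triplet regimen versus SOC regimen (regorafenib) in 3L" and later lines. Section 7.2 says: "Part 2 is a randomized open-label study with 2 treatment arms, nivolumab + ipilimumab + trametinib versus regorafenib". It assigns treatment 2:1 within strata of primary tumor sidedness and extended RAS status. Section 5.1.3 gives the arm sizes as "approximately 80 participants to receive the triplet regimen and 40 participants to receive the SOC therapy, regorafenib" and bars crossover. The primary efficacy population for Part 2 is all randomized participants (Sections 10.2 and 10.3.1).

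The endpoint table in Section 10.3.1 has three method cells:
- ORR and DCR: "Estimate of ORR/DCR and corresponding two-sided exact 95% CI using the Clopper-Pearson method by treatment".
- DOR and TTR: a Kaplan-Meier median with 95% CI, again by treatment.
- PFS and OS: "Estimate of median and rates at fixed time points by the Kaplan-Meier method", with 95% CIs, again by treatment.

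Tumor sidedness appears in the visible analysis text only as an example of a subgroup. RAS does not appear there.

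Two statements limit what can be read into the table. Section 10.3 introduces it with "Below is a summary of planned statistical analyses of the primary and secondary endpoints", and Section 10.3.1 adds that "additional analyses will be described in the SAP".

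**The concern.** The design pays for a comparison. It has a concurrent control, 2:1 allocation, two stratification factors, a randomized analysis population and no crossover. The visible methods then describe the two arms one at a time. No cell yields a difference in ORR or DCR or a hazard ratio, and no cell carries the stratification factors into an arm contrast.

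If the report follows those cells, regorafenib serves as a second single-arm series. A reader could compute a crude ORR or DCR difference from the published counts. The stratified difference and the hazard ratios would be out of reach, because medians and a few landmark rates do not determine them. Readers would probably compare the two sets of confidence intervals by eye, which is a poor guide to the size and precision of the treatment difference.

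**Working it through.** **The plan's own figure.** 120 x 2/3 = 80 and 120 x 1/3 = 40, which matches Section 5.1.3. No alpha, power or target effect is visible for Part 2, so there is no power figure to reproduce.

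**Per-arm intervals against a contrast.** Take 13/80 and 1/40 as an illustration.
- Clopper-Pearson: 13/80 gives 8.9-26.2% and 1/40 gives 0.1-13.2%. They overlap.
- Difference: 16.25 - 2.50 = 13.75 points.
- Wilson limits for Newcombe's method: 9.75-25.84% and 0.44-12.88%.
- Lower limit: 13.75 - sqrt[(16.25 - 9.75)^2 + (12.88 - 2.50)^2] = 13.75 - 12.25 = 1.5.
- Upper limit: 13.75 + sqrt[(25.84 - 16.25)^2 + (2.50 - 0.44)^2] = 13.75 + 9.81 = 23.6.

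The result depends on the counts:

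| Triplet /80 vs regorafenib /40 | Difference (points) | Newcombe 95% CI |
|---|---|---|
| 12 vs 0 | 15.0 | 4.3 to 24.4 |
| 12 vs 1 | 12.5 | 0.4 to 22.1 |
| 8 vs 0 | 10.0 | -0.01 to 18.5 |
| 9 vs 1 | 8.8 | -2.9 to 17.8 |
| 13 vs 2 | 11.3 | -2.0 to 21.5 |

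**Hazard-ratio precision.** SE(log HR) = sqrt(1/e1 + 1/e2), where e1 and e2 are the events per arm. The 95% CI is the HR times or divided by exp(1.96 x SE). Event fractions of 60% and 90% are assumed.
- 60%: 48 and 24 events, SE 0.250, factor 1.63.
- 90%: 72 and 36 events, SE 0.204, factor 1.49.

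Within RAS groups at the 65/35 target of Section 5.1, the factor is 1.84 to 1.64 for mutant (SE 0.310 to 0.253) and 2.29 to 1.97 for wild-type (SE 0.423 to 0.345).

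A simulation of the stratified Cox model at 80/40 used 3,000 trials, HR 1 or 0.67, control median 1.9 months, 8-week scans and 75-83% events. It gave a factor of 1.54-1.57 with coverage near 95%.

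**DCR precision.** Half-width = 1.96 x sqrt[p1(1 - p1)/80 + p2(1 - p2)/40]. With regorafenib DCR p2 assumed at 30-45% and a true difference of 0 or 15 points, this is 17 to 19 points. In simulation over four strata (20,000 trials per setting, 25-45% right-sided assumed), the Mantel-Haenszel difference with the Sato variance covered 94.0-94.5%.

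**Why ORR should stay unstratified.** Table 3.2.2-1 gives a regorafenib response rate of 1%.
- P(0 of 40) = 0.99^40 = 0.669.
- P(1 of 40) = 40 x 0.01 x 0.99^39 = 0.270.
- The sum is 94%. At 3% it is 0.296 + 0.366 = 66%.

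Spread over four strata, so few responders make a stratified estimate fragile. In simulation at true rates of 5% versus 1%, Mantel-Haenszel coverage for ORR fell to 91.5%.

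**Why one interval must be named.** At 8/80 versus 0/40, Newcombe gives -0.01 to 18.5 and Miettinen-Nurminen gives 0.9 to 18.6. One includes zero and the other does not.

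**The case against.** The strongest reply is that absence is not shown. The table is only a summary, and Section 10.3 says "The statistical analysis plan will be developed and finalized before the first database lock". That separate SAP is not in the published text. Section 10.1.2 is partly redacted, and several Section 10.3 headings in the table of contents are blacked out. One table also serves the single-arm parts, so the by-treatment wording may simply be generic. This stands. A reader might infer that the sponsor planned no comparison of the arms, and the documents do not support that.

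The second reply is that the methods fit the stated aims. Table 4-2 asks for the ORR in each treated group, and Section 10.1.2 speaks of preliminary efficacy. No visible hypothesis is contradicted. This also stands, and it rules out another tempting reading, that Part 2 needs a formal test, an alpha or a power claim. It does not argue against an effect estimate with an interval, and no visible sentence says the arms will not be contrasted.

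Third, the gain for the primary endpoint is small, because anyone can compute the crude ORR difference from the counts. That is true. The main gain is in the hazard ratios and the stratified DCR difference.

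Fourth, Section 5.4.3 gives a prognostic basis only for sidedness and calls the prognostic value of KRAS unclear. So the case for stratifying the analysis by RAS is that RAS was used to balance the arms, and not that it is known to be prognostic.

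**Conclusion.** The point holds as a statement about the visible text. Every method cell in Section 10.3.1 is per-arm, while Part 2 is a stratified 2:1 randomized evaluation of triplet versus regorafenib. It is a worthwhile, low-cost improvement and not the correction of an error.

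The size of the loss is the missing set of estimates: PFS and OS hazard ratios with intervals of about the HR times or divided by 1.5-1.6, and a DCR difference known to about 17-19 points either way. These figures rest on the planned 80 and 40 and on assumed event fractions and DCRs. The ORR example shows that overlapping exact intervals can accompany a difference whose interval excludes zero. It does not show that this will happen here, and several nearby counts give intervals that include zero.

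**What to change.** For the Part 2 randomized population, keep the per-arm summaries and add the following, labelled as estimation with no test or alpha claim:

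1. PFS and OS hazard ratios with 95% CI from a Cox model stratified by sidedness and extended RAS.
2. The DCR difference, triplet minus regorafenib, with 95% CI, using Mantel-Haenszel weights over the two randomization factors and the Sato variance.
3. The ORR difference with an unstratified Newcombe 95% CI, used whatever the responder counts, so that neither the estimator nor the interval is chosen after seeing the data.

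Show any within-RAS or within-sidedness contrasts as descriptive only.

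If the SAP already contains these estimates, a citation in Section 10.3.1 is enough. If not, date the addition, state that it followed the close of enrollment on 30-Nov-2022 in an open-label trial, and state whether by-arm results had been seen. The interim analysis in Section 10.3.7 and the emerging data cited for Amendment 04 make that disclosure necessary. A bare statement that Part 2 is descriptive would be honest but would still leave the randomization unused.

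The cost is a few lines of SAP text and standard programming, with no new data. The downsides are wide intervals and an analysis that, if added now, is not clean prespecification.

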4 OBJECTIVES AND ENDPOINTS

Table 4-1: Objectives and Endpoints: Parts 1 and 1A

Objectives	Endpoints
Primary	

To characterize the safety and tolerability of combination therapiesTo establish recommended dosing regimen for the combination (nivolumab plus ipilimumab plus trametinib OR nivolumab plus trametinib)	
DLTs in Part 1 and Part 1A, only, observed for 1 treatment cycle (4 weeks for the doublet regimen and 8 weeks for the triplet regimen)Safety (including but not limited to): AEs, SAEs, deaths, and clinical laboratory abnormalities per CTCAE (version 4.0)
Secondary	

To evaluate preliminary efficacy	
ORR DCR, DOR, TTR, and PFS by investigator per RECIST v1.1OS

AE, adverse event; CTCAE, Common Terminology Criteria for Adverse Events; DCR, disease control rate; DLTs, dose limiting toxicities; DOR, duration of response; [REDACTED]; ORR, objective response rate; OS, overall survival; PFS, progression free survival; [REDACTED]; RECIST, Response Evaluation Criteria in Solid Tumors; SAE, serious adverse event; TTR, time to response.

Table 4-2: Objectives and Endpoints: Parts 1B and 2

Objectives	Endpoints
Primary 
To evaluate the ORR in all participants treated with nivolumab plus ipilimumab and trametinib in the 2L and 3L+^a setting (Parts 1B and 2, respectively) and regorafenib in 3L+^a (Part 2 only)	
ORR by investigator^b
Secondary 
To evaluate efficacy in all participants treated with nivolumab plus ipilimumab and trametinib in the 2L and 3L+^a setting (Parts 1B and 2, respectively); and regorafenib in 3L+^a (Part 2 only) [REDACTED] [REDACTED]	
BOR, DCR, DOR, TTR, and PFS by investigator^bOS

To characterize the safety and tolerability of combination therapies	
Safety (including but not limited to): AEs, SAEs, deaths, and clinical laboratory abnormalities per CTCAE (version 4.0)

Table 4-2: Objectives and Endpoints: Parts 1B and 2

Objectives	Endpoints

AE, adverse event; [REDACTED], BOR, best overall response; [REDACTED]; CTCAE, Common Terminology Criteria for Adverse Events; DCR, disease control rate;; DOR, duration of response; [REDACTED]

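### Does naming only the Greenwood formula for Kaplan-Meier rates leave their 95% intervals with poor coverage?

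*Combined protocol and SAP*

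**What the plan says.** The PFS and OS row of the table in Section 10.3.1 plans an "Estimate of median and rates at fixed time points by the Kaplan-Meier method", with "corresponding two sided 95% CI using log-log transformation (for median) and Greenwood formula (for rates) by treatment". The log-log scale is therefore tied to the median, and the rates get only the name of a variance formula. The landmark times are not listed.

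Section 10.3 introduces this material with "Below is a summary of planned statistical analyses of the primary and secondary endpoints" and says an SAP will be finalized before the first database lock. Section 10.3.1 adds: "Details on censoring scheme on time-to-event endpoints such as DOR, PFS, and OS and additional analyses will be described in the SAP". The text supplied contains no separate SAP.

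In Part 2, Section 5.1.3 plans for "approximately 80 participants to receive the triplet regimen and 40 participants to receive the SOC therapy, regorafenib". Table 4-2 lists "BOR, DCR, DOR, TTR, and PFS by investigator", together with OS, as secondary for Parts 1B and 2. The primary endpoint, ORR, has an exact Clopper-Pearson interval.

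**The concern.** The sentence sets two methods side by side: a transformation for the median and Greenwood for the rates. Read by contrast, it suggests that the rates are not transformed. An untransformed interval does badly when the true rate is low and the sample small, because the sampling distribution is skewed. Coverage falls below 95% and the lower limit can be negative, which is impossible for a probability.

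The regorafenib arm fits that description. It has about 40 participants and a short expected PFS, so a 6-month PFS rate could be little more than 10%. At stake would be a published 95% interval for the control arm that covers less often than it claims, in the only randomized part of the study.

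**Working it through.** **Inputs from the protocol**
- Regorafenib arm: 120 × 1/3 = 40; triplet arm 80 (Sections 5.1.3 and 10.1.2).
- Regorafenib median PFS 1.9 months and median OS 6.4 months (Table 3.2.2-1).
- Second PFS anchor (Table 3.3.1-1): the cobimetinib-atezolizumab trial gives a median of 1.91 months and a hazard ratio against regorafenib of 1.25 (95% CI 0.94 to 1.65). If exponential, the regorafenib median is 1.91 × 1.25 = 2.39 months; over the CI, 1.91 × 0.94 = 1.80 to 1.91 × 1.65 = 3.15 months.
- Second-line median PFS 6 to 7 months (Table 3.2.2-1), applied to Part 1B with n = 80.

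**Assumptions not in the protocol:** exponential curves, and landmarks at 4 and 6 months.

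The protocol gives no coverage figure for these intervals, so there is none to reproduce.

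**Formulas.** With no censoring before the landmark, the Kaplan-Meier estimate is S = x/n and Greenwood's variance is S(1 − S)/n.
- Plain: S ± 1.96 × SE.
- Log-log: S^exp(±1.96θ), with θ = SE/(S × |ln S|).

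Coverage is the sum of Binomial(n, true rate) probabilities over outcomes whose interval contains the true rate. The outcome x = 0 counts as a miss for both methods. Where a range of rates is given, coverage is averaged over an even grid of 1,001 points.

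**Worked case, 2 of 40 progression-free.** S = 0.05, SE = √(0.05 × 0.95/40) = 0.0345, θ = 0.0345/(0.05 × 2.996) = 0.230. Plain: −1.8% to 11.8%. Log-log: 0.9% to 14.8%. The plain lower limit is negative for x = 1, 2 or 3 and positive from x = 4 (0.7%).

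**Rates.** 6 months: 2^(−6/1.9) = 11.2% to 2^(−6/2.39) = 17.5%. 4 months: 23.2% to 31.3%.

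| Setting | Plain | Log-log |
|---|---|---|
| n = 40, 6-month PFS, 11.2% to 17.5% | 91.2% (range 86% to 95%) | 95.2% (92% to 98%) |
| n = 40, 6-month PFS over the hazard ratio CI, 9.9% to 26.7% | 92.3% | 95.2% |
| n = 40, 4-month PFS | 93.2% | 95.1% |
| n = 80, rates 11.2% to 17.5% | 93.2% | 95.1% |
| n = 40, 6-month OS, 52% | 94.2% | 93.9% |
| n = 80, Part 1B 6-month PFS, 50% to 55% | 94.5% | 95.1% |

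At single rates with n = 40, coverage jumps because outcomes are discrete. Plain against log-log is 93.7% and 98.0% at 11.2%, 86.8% and 94.4% at 12%, 93.9% and 93.9% at 15%, and 92.1% and 96.4% at 17.5%. A negative plain lower limit occurs in 6% to 32% of trials over the range 11.2% to 17.5%, and in under 1% at the 4-month landmark.

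**Censoring (simulated, n = 40, rates 11.2% to 17.5%).** With 10% of participants censored before the landmark, the averages are 90.9% plain and 95.4% log-log; with 20%, 89.7% and 94.2%. Log-log is not a cure everywhere. At 7 months (true rate 7.8%, median 1.9 months) with a censoring rate of 0.08 per month, plain covers 86.2% and log-log 84.5%. The curve reaches zero in 13% of runs, and no log-log interval then exists.

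**The case for a change.** The strongest case for a change is that the fix is one phrase and the shortfall is real under a natural reading. Calling the section a summary does not fully answer it. What Section 10.3.1 sends to the SAP is other subgroups, censoring details and additional analyses; the interval method for rates is set in the table itself. An SAP author who copied the table could carry an untransformed interval forward and print a negative limit for the control arm. Small subgroups would make this worse.

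The arithmetic in that case stands, and so does the observation that the scale is unstated. Two things do not. First, the table does not say the interval is untransformed. Greenwood's variance is also the variance used in a log-log interval, so the sentence is as compatible with the better method as with the weaker one. Second, 91% is not a property of any one design point. It is an average over a range whose upper end is inferred from a hazard ratio in another trial. At the only directly stated median (1.9 months, rate 11.2%), the plain interval at 93.7% is closer to 95% than log-log at 98.0%. With scans every 8 weeks, a 1.9-month median also falls at about the first scan, so a smooth exponential tail to 6 months is itself a weak extrapolation.

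**Conclusion.** This is a missing detail that an analyst fills sensibly, and it calls for no change to the plan. Log-log is already the chosen scale for the median, and using it with Greenwood's variance for the rates is an ordinary software option. Interval scale and landmark times are normal SAP content and can be written down there.

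If the untransformed interval were used, average coverage would be about 91% to 93% for low landmark PFS rates in the 40-participant arm without censoring, or about 90% with 20% censored early. Lower limits would sometimes be negative. Mid-range rates such as 6-month OS or Part 1B PFS would be almost unaffected. All of this rests on assumed landmarks and exponential curves.

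No conclusion depends on it. PFS and OS are secondary, Section 10.3.1 gives only estimates and intervals by treatment, no stated test or decision rule uses a landmark rate, and the primary ORR interval is exact.
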